3.5 Secondary Study Endpoints

Secondary endpoints will detail extent of alcohol cravings and relapse during treatment with acamprosate for treatment of AUD in alcohol-related liver disease as measured by Pennsylvania Alcohol Craving Scale (PACS) scores and reporting of any amount of alcohol use.

3.6 Primary Safety Endpoints

See 3.4.

3.7 Identification of Source Data

The following source data will be directly recorded on the Case Report Form (CRF):

- Vital signs
- Weight
- Clinical history
- Adverse events
- Medication list including new medications, change in medications
- Alcohol use
- Other substance use including nicotine and recreational drug use
- PACS responses and score
- MMSE responses and score
- West Haven HE grade
- Laboratory results and clinical interpretation of the values.
- Clinical significance of observations (when applicable)

The following source data will not be directly collected in the Case Report Form (CRF), but will be captured in supportive documentation (Demographics form, Concurrent Medications form):

- All data to be obtained at enrollment as detailed in 6.1.

4 Subject Selection Enrollment and Withdrawal

4.1 Inclusion Criteria

Eligible individuals:

- Aged 21 or over
- Diagnosis of alcohol-related liver disease and AUD.
 - The diagnosis of alcohol-related liver disease will be determined by a hepatologist based on history of regular and excessive alcohol consumption in the absence of other causes of liver cirrhosis or acute hepatitis, compatible clinical, imaging and laboratory findings and typical histology on liver biopsy, if performed. Underlying liver disease may include alcoholic hepatitis, advanced (F3-F4) fibrosis, and/or portal hypertension.
 - The diagnosis of AUD will be determined by a hepatologist and/or addiction psychiatrist based on history obtained that is consistent with DSM-5 diagnostic criteria for AUD (all categories of mild, moderate and severe considered eligible) (American Psychiatric Association, 2013; questions from NIH, 2016).

- Patients need not be abstinent from alcohol prior to initiating acamprosate treatment (but not abstinent for more than 6 months).
- At study enrollment, initial MELD-Na score must be less than 20 for the five individuals enrolling in the first phase of the pilot safety assessment. The second phase of the pilot safety assessment will include individuals with a MELD-Na of 20 or more at enrollment.
- Have capacity to provide consent themselves

4.2 Exclusion Criteria

Exclusion criteria:

- Individuals with a glomerular filtration rate (GFR) of less than 30 ml/min
- Congestive heart failure (NYHA class II or higher)
- Hypotension, requiring the use of vasoconstrictors (i.e. midodrine)
- Pregnancy, lactation or refusal to use a reliable method of birth control if a sexually active female of childbearing potential. Although no human trial data is available, animal studies suggest possible teratogenic effects of acamprosate (Merck, 2005).

4.3 Subject Recruitment, Enrollment and Screening

Patients will be identified in the outpatient hepatobiliary clinic or while admitted to hospital and seen by the gastroenterology or hepatobiliary service at Mayo Clinic, Rochester. This population is evaluated for potential eligibility for other alcohol-related liver disease studies by a research coordinator on a weekly basis. Physicians that identify eligible patients that are not captured by the research coordinator may refer the patient. Both male and female subjects must use 2 reliable forms of birth control from screening to at least up to 4 weeks after the study treatment is over. No recruitment material will be created.

Using clinical information obtained from the electronic medical record, patients will be screened for eligibility. Documentation of inclusion and exclusion criteria will be included in the participant database.

4.4 Early Withdrawal of Subjects

4.4.1 When and How to Withdraw Subjects

Patients will be withdrawn from the study prior to study completion if:

1. Subjects elect to withdraw consent
2. Subject is found to be ineligible for the protocol as per the Inclusion/Exclusion criteria.
3. Subjects experience a serious adverse event felt to possibly be related to acamprosate administration as determined by PI and/or DSMB.
4. Failure of the subject to comply with protocol requirements.
5. Exhibition of unacceptable toxicity which would make it difficult or dangerous to comply with further protocol requirements such as study visits, blood draws, etc.
6. There are changes in medical status of the subject such that the Investigator believes that subject safety will be compromised or that it would be in the best interest of the subject to stop participation in the study.

7. Death of the subject.
8. Subjects with a test consistent with pregnancy such as a positive beta-hCG.
9. Subject is lost to follow-up.
10. Any complication that requires prolongation of the hospitalization or change in treatment and in the opinion of the investigator is related to the study drug.

If subjects are withdrawn from the study, they will be replaced to ensure a total of 10 patients complete the study in its entirety. The data collected up until the time of withdrawal from the study will be included in analysis.

Follow up from subjects withdrawn from study treatment will include:

- Clinic visit at time of withdraw from study will be recommended. Beyond risk of returning to alcohol consumption, sudden study treatment termination should not include any subject safety considerations.
- Follow up phone call 3 months after withdrawal from study

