This study is a phase IIa trial of the safety of acamprosate in treating AUD in alcohol-related liver disease. Subjects will be screened for eligibility at outpatient clinic visits and during hospitalizations; interested qualified subjects will be consented and offered participation in this trial. At study enrollment, initial MELD-Na score must be less than 20 for the five individuals enrolling in the first phase of the pilot safety assessment. The second phase of the pilot safety assessment will include individuals with a MELD-Na of 20 or more at enrollment. Once consent has been obtained, baseline characteristics will be established and then patients will be initiated on acamprosate treatment. Acamprosate will be administered for three months, during which time, patients will complete monthly blood work, weekly telephone assessments for the first month, followed by telephone assessments and urine testing on a monthly basis thereafter. A final clinic visit for evaluation and collection of lab samples will be conducted at the end of the study at 3 months. Patients will be contacted by telephone at weeks 13 and 24 after study enrollment for final follow up assessments off of study medication.

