Study duration will be six months. During the study, patients will complete monthly MELD-Na labs and receive a phone call weekly for the first month, then monthly for a total of 3 months. Urine ethyl glucuronide will be done at enrollment and once monthly. Patients will then have a follow up visit at 12 weeks, with labs, urine ethyl glucuronide, vital signs and physical exam. During telephone assessments and at the follow up visit, patients will be asked about potential side effects and hepatic decompensation. Other variables to be collected at enrollment and at the 3 month visit include Child-Pugh score, West Haven grading of HE, vital signs at enrollment and current medications. At enrollment, during phone calls and at the follow up visit, patients will be asked standardized questions to assess for HE based on the abbreviated telephone version of the mini-mental state examination (MMSE). Follow up telephone visits at 13 and 24 weeks will be conducted, primarily to monitor for adverse events and alcohol relapse.

The Pennsylvania Alcohol Craving Scale (PACS) will be applied before treatment initiation, weekly for the first month on treatment, then monthly thereafter. This will include the need severity scale (mild, moderate, severe) at baseline and at each assessment by phone call and in clinic.

Alcohol use relapse will be monitored. Any amount of alcohol use as revealed during follow-up considered a relapse event. Alcohol use will be captured and categorized as none, slip (no longer drinking at most recent follow up) or sustained alcohol use (minimum 100 days drinking). Slips and sustained alcohol use will be categorized as binge drinking, frequent drinking, or both (binge drinking as more than 6 units/day for men and 4 units/day for women and frequent drinking as alcohol use in 4 or more days/week regardless of quantity per day) (Lee et al., 2018).

Basic descriptive statistics and a qualitative analysis will be performed. Analyses will be performed using SPSS 25 (Chicago, IL). Results will not contain any patient-specific information.

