5.4 Preparation and Administration of Study Drug

Subjects will collect the study drug from their local pharmacy and self-administer by mouth.

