6.1 Visit 1 – Screening/enrollment day

Informed consent will be obtained. Inclusion and exclusion criteria will be evaluated. Collected baseline characteristics will include patient age, sex, race, marital and employment status, education level, social support, presence of children, age of children, underlying liver disease etiology, MELD-Na score, presence of ascites, esophageal varices, spontaneous bacterial peritonitis, diabetes, corticosteroid or other medical treatment for alcoholic hepatitis (Maddrey and Lille scores if relevant), medical comorbidities, prescription and non-prescription medications. With regard to alcohol use, patients will fill out the Alcohol Use Disorder Identification Test (AUDIT) and the following history will be obtained: duration of excess alcohol consumption in years, level of alcohol consumption prior to study enrollment, interval of alcohol abstinence prior to study enrollment, family history of alcoholism, history of alcohol-related legal issues, psychiatric comorbidity (requiring medication, outpatient care or hospitalization), other addictions including smoking and number of prior rehabilitation attempts for alcohol or other addictions. The PACS questionnaire will be administered.

Vital signs and a physical examination will be performed. West Haven HE score will be graded and modified telephone version of MMSE completed. Blood work will be completed including a complete blood count, electrolytes, creatinine, blood urea nitrogen, total bilirubin, direct bilirubin, albumin, INR, AST, ALT and alkaline phosphatase. A urine ethyl glucuronide will be performed. A urine pregnancy test will be conducted before admission into the trial for women of child-bearing potential.

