6.2 Visit 2-5

Visits 2-5 will be conducted by telephone and include data to be included on the Case Report Form including

- Clinical history
- Adverse events
- Medication list including new medications, change in medications
- Alcohol use
- Other substance use including nicotine and recreational drug use
- PACS responses and score
- MMSE responses and score
- West Haven HE grade
- Laboratory results and clinical interpretation of the values.
- Clinical significance of observations (when applicable)

6.3 Visit 6

Visit 6 will occur at week 12 of acamprosate therapy. Interval clinical history, adverse events, medication list and alcohol and other substance use will be detailed. PACS score will be evaluated. Case Report Form will be completed.

Vital signs and a physical examination will be performed. West Haven HE score will be graded and modified telephone version of MMSE completed. Blood work will be completed including a complete blood count, electrolytes, creatinine, blood urea nitrogen, total bilirubin, direct bilirubin, albumin, INR, AST, ALT and alkaline phosphatase.

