8.2 Recording of Adverse Events

At each contact with the subject, the study team must seek information on adverse events by specific questioning and, as appropriate, by examination. Information on all adverse events should be recorded immediately in the source document, and also in the appropriate adverse event section of the case report form (CRF). All clearly related signs, symptoms, and abnormal diagnostic, laboratory or procedure results should be recorded in the source document.

All adverse events occurring during the study period will be recorded. The clinical course of each event should be followed until resolution, stabilization, or until it has been ultimately determined that the study treatment or participation is not the probable cause. Serious adverse events that are still ongoing at the end of the study period will be followed up to determine the final outcome. Any serious adverse event that occurs during the Adverse Event Reporting Period and is considered to be at least possibly related to the study treatment or study participation will be recorded and reported immediately.

Adverse events will be classified per the CTCAE Version 5.0, November 27, 2017.

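### One pregnancy test is scheduled before admission and none during 12 weeks of home dosing, so on treatment the pregnancy withdrawal rule depends on self-report or an unscheduled test

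*Combined protocol and SAP*

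**What the plan says.** All references are to the combined protocol and SAP.

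- **Hazard.** Section 4.2 excludes pregnant women and gives a reason: "animal studies suggest possible teratogenic effects of acamprosate".
- **Action on pregnancy.** Section 4.4.1, criterion 8, withdraws "Subjects with a test consistent with pregnancy such as a positive beta-hCG".
- **Testing.** Section 6.1 states: "A urine pregnancy test will be conducted before admission into the trial for women of child-bearing potential". Section 3.1 describes the same single test.
- **Contacts on treatment.** Section 6.2 says: "Visits 2-5 will be conducted by telephone and include data to be included on the Case Report Form". It then itemises their content, and section 6.3 does the same for Visit 6 at week 12. Neither list includes a pregnancy test, nor do sections 6.4 and 6.5 for weeks 13 and 24.
- **Dosing.** Section 5.4 says: "Subjects will collect the study drug from their local pharmacy and self-administer by mouth".
- **Urine on treatment.** Section 3.1 says: "Urine ethyl glucuronide will be done at enrollment and once monthly". No other repeated urine test is named.
- **Other safeguards.** Section 4.3 requires two forms of contraception of both sexes, until at least 4 weeks after treatment. Section 8.2 says: "At each contact with the subject, the study team must seek information on adverse events by specific questioning". Criterion 6 in section 4.4.1 lets the investigator withdraw a subject when a change in medical status threatens safety.

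**The concern.** The plan treats fetal exposure as a hazard and has a rule for acting on a positive test, but it schedules no test that could trigger the rule once dosing has begun. If contraception fails and the woman does not yet know, or does not say, no scheduled check stops the drug before week 12. The same holds if she conceived too recently for the admission test to show it. Before week 12 the study contacts described are telephone calls, so an unrecognised pregnancy is unlikely to be found by examination.

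What is at stake is the safety of a small and unknown number of participants and pregnancies. The analysis is descriptive (section 7.2), and nothing in it depends on this point.

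**Working it through.** **Step 1: count the scheduled tests.** The plan gives no figure of its own to reproduce.

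| Period | Source | Pregnancy tests |
|---|---|---|
| Before admission | 3.1, 6.1 | 1 |
| Visits 2-5, telephone | 6.2 | 0 |
| Visit 6, week 12 | 6.3 | 0 |
| Visits 7 and 8, weeks 13 and 24 | 6.4, 6.5 | 0 |

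The schedule table is not used as evidence. It has no pregnancy-test row at all, so it omits even the baseline test that the text requires.

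**Step 2: bound the exposure.** This step needs an assumption that is not in the documents: the lag L from conception to a positive urine test, taken as 2 weeks (range 1.5 to 3). The admission test is placed at week 0, and dosing is taken to stop on the day of a positive test. Let c be the week of conception, from -L to 12. Dosing ends at T, the first scheduled test at or after c + L, or week 12 if there is none.

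Exposure = T - max(c, 0)

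The worst case is a conception just too late for one test to show.

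- *Plan as written (week 0 only):* c just after -L gives T = 12, so exposure = 12 - 0 = 12 weeks for any L.
- *Tests added at weeks 4 and 8:* c just after -L gives 4 - 0 = 4. For c just after 4 - L, exposure is 8 - (4 - L) = 4 + L. For c just after 8 - L, it is 12 - (8 - L) = 4 + L. The maximum is 4 + L, which is 5.5, 6 and 7 weeks for L = 1.5, 2 and 3.
- *Week 4 only:* 12 - (4 - L) = 8 + L, which is 9.5, 10 and 11 weeks.
- *Week 8 only:* c just after -L gives 8 - 0 = 8, which exceeds 4 + L for every L in the range, so the maximum is 8 weeks.
- *Weeks 4, 8 and 12:* dosing ends at week 12 anyway, so the maximum stays at 4 + L.

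These are upper bounds for a stop by scheduled test or end of treatment. They are not expected exposures.

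**Step 3: count the added tests.** The number of women of childbearing potential among the 10 completers is not given, so it ranges from 0 to 10. Two tests each gives 2 × 0 = 0 to 2 × 10 = 20 extra tests. Three each, with week 12, gives 0 to 30.

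**The case against.** The strongest reply is that this is a preference and not an error. Nothing in the plan sets a testing frequency or an exposure limit that it then misses. The safeguards are layered: exclusion of pregnancy, a test before admission, two contraceptive methods, adverse-event questioning at every contact, and withdrawal on any information or any test. The gap is confined to a woman who conceives despite contraception, or too recently for the admission test, and does not know or say so through the calls at weeks 1 to 4 and 8. That narrows the point, and it means no target in the documents makes two tests necessary. It does not close the gap, because none of the on-treatment safeguards detects a pregnancy that the woman has not recognised.

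A second reply is that the visit texts are not complete lists. Section 6.3 omits the ethyl glucuronide test that section 3.1 places at the 12-week visit, and the case report form is an attachment not shown here. This stands, and it limits confidence in the zero count to medium.

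Two stronger readings are tempting:

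- A reader might infer that criterion 8 is inoperable or contradicts the schedule. It is valid as written, since it does not require the test to be a study test.
- A reader might infer that sections 4.2 and 4.3 conflict, because 4.2 asks for one method from sexually active women who could conceive while 4.3 asks for two from both sexes. A subject who meets 4.3 meets both. Carrying the unrestricted 4.3 rule into the exclusions could bar people who cannot conceive or are not sexually active, so no change to 4.2 is proposed.

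**Conclusion.** The point holds as a small patient-safety gap that is worth closing but not essential. What the documents support is one scheduled pregnancy test before admission and none on treatment.

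The fall in the bound from 12 weeks to about 6 (5.5 to 7) rests on the assumed lag of 1.5 to 3 weeks and is conditional on a conception whose probability cannot be estimated from the plan. It would be wrong to read 12 weeks as the exposure to expect. The benefit may be zero, because the plan does not say how many women of childbearing potential will enrol. The safety and craving summaries are unaffected.

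**What to change.** In section 6 and the schedule table, add a urine pregnancy test at weeks 4 and 8 for women of childbearing potential, with a positive result stopping the drug under criterion 8. Section 6.2 alone may not be the right place: it covers four visits, while the table shows five calls before week 12 (weeks 1 to 4 and 8), so week 8 may fall outside it.

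Run the test on the monthly urine already planned for ethyl glucuronide. The documents do not say where that urine is collected. If the sample cannot be shared, use a home test with the result taken at the week 4 and week 8 calls. This fallback still relies on the woman's report of the result, but it prompts a test that would otherwise not be done.

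A week 12 test is optional. It would identify an exposed pregnancy for follow-up but would not shorten exposure.

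The cost is a protocol amendment and at most two extra urine tests per eligible woman (three with week 12), with no extra visits if the sample is shared or the home test is used.

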Acamprosate has not been evaluated formally in individuals with AUD and liver disease. It is an N-methyl-D-aspartate glutamate receptor antagonist approved by the Food and Drug Administration to aid in maintaining abstinence in individuals with alcohol dependence (Frye et al., 2016). Acamprosate has an unclear mechanism of action, although it is thought that its effect on decreased alcohol craving intensity is mediated through a reduction in glutamate levels (Frye et al., 2016). The efficacy of acamprosate has been demonstrated in several meta-analyses, most recently exhibiting a number needed to treat of 12 to prevent return to any drinking (Jonas et al., 2014; Rosato et al., 2015). Acamprosate is not metabolized by the liver and thus has been considered as a potential therapeutic option in those with liver disease. However, as acamprosate antagonizes the glutamate receptor, there have been concerns it may increase the risk of hepatic encephalopathy. Previously, a single dose of acamprosate 666 mg was administered to 12 patients with Child-Pugh A or B cirrhosis with no identifiable induction of subclinical hepatic encephalopathy; however, transient diastolic hypotension was noted (Delgrange et al., 1992). No further studies on acamprosate have been performed in individuals with liver disease.

To evaluate the safety of acamprosate in individuals with AUD and alcohol-related liver disease, an initial pilot study in five patients with a Model for End Stage Liver Disease Sodium (MELD-Na) score less than 20 will be conducted. If no safety concerns are identified, the study will then

be performed in five patients with MELD-Na scores of 20 or more. If again no safety concerns are identified, a larger, placebo-controlled efficacy study is planned and will be submitted as a separate protocol.

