3.1 General Description

Adult patients aged 21 or over with a diagnosis of alcohol-related liver disease and AUD will be identified in the outpatient clinic or while admitted to hospital and seen by the gastroenterology or hepatobiliary service at Mayo Clinic, Rochester. This population is evaluated for potential eligibility for other alcohol-related liver disease studies by a research coordinator on a weekly basis. The diagnosis of alcohol-related liver disease will be determined by a hepatologist based on history of regular and excessive alcohol consumption in the absence of other causes of liver cirrhosis or acute hepatitis, compatible clinical, imaging and laboratory findings and typical histology on liver biopsy, if performed. Underlying liver disease may include alcoholic hepatitis, advanced (F3-F4) fibrosis, and/or portal hypertension. The diagnosis of AUD will be determined by a hepatologist based on history obtained that is consistent with DSM-5 diagnostic criteria for AUD (all categories of mild, moderate and severe considered eligible).

Patients need not be abstinent from alcohol prior to initiating acamprosate treatment (but not abstinent for more than 6 months). At study enrollment, initial MELD-Na score must be less than 20 for the five individuals enrolling in the first phase of the pilot safety assessment. The second phase of the pilot safety assessment will include individuals with a MELD-Na of 20 or more at enrollment. Patients with heart failure (NYHA class II or higher) or hypotension requiring the use of vasoconstrictors (i.e. midodrine) will be excluded. Individuals with a glomerular filtration rate (GFR) of less than 30 ml/min will be excluded. Acamprosate will be dosed at 333 mg TID, increased to 666 mg TID after 1 week if tolerated. If GFR is 30-50 ml/min, dosage will remain at 333 mg TID throughout the study. Acamprosate will be administered for a total of 3 months.

Prior to enrollment, known risks and benefits of acamprosate in treating AUD will be discussed with patients including pruritus (4%), diarrhea (10% to 17%), flatulence (3%), nausea (4%), dizziness (3%), insomnia (7%), anxiety (6%) and depression (5%). More rare risks include cardiomyopathy, deep thrombophlebitis, heart failure, mesenteric arterial occlusion, shock and suicidal intent (1%).

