3.2 Number of Subjects

10 individuals.

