8.5 Stopping Rules

The study will stop for an individual patient if any of the following occur:

1. The participant decides to withdraw from the study.
2. The participant experiences a Serious Adverse Event (SAE) that, in the opinion of the investigator, is possibly, probably or definitely related to the study drug utilizing the National Cancer Institute's CTCAE system as a guide.
3. The participant experiences a UPIRTSO AND, in the opinion of the investigator and study adjudicator, is related to the study drug
4. The participant experiences a grade 3 or higher CTCAE develop that are determined to be possibly or likely attributable to study drug
5. The participant experiences a medical condition that, in the opinion of the investigator, continuation on the study drug would be detrimental.
6. Decision by the DSMB. If a participant experiences a MELD-Na score increase by more than 5 points from baseline or doubling bilirubin level from enrollment, the DSMB will review the records to determine whether DILI is suspected or changes are attributed to natural course of disease
7. The participant experiences an increase of AST or ALT >500 U/L

Determination of whether worsening of liver biochemical tests is due to the alcoholic hepatitis or study drug induced liver injury (DILI) is difficult. An AST or ALT increase >500 IU/L would be considered an indication that the patient might have DILI since AST and ALT are typically < 300-400 U/L in AH. Such an increase of > 500 IU/L would trigger prompt evaluation and consideration of discontinuation of the study drug. Considering how difficult it is to distinguish potential DILI from worsening of the underlying liver disease, we have incorporated an external adjudication of all suspected DILI events. An increase in MELD-Na score >5 points from baseline, or doubling bilirubin (2 times the baseline level at enrollment) would warrant urgent review by the DSMB.

The study will be put on hold for review with the DSMB if one patient experiences a serious adverse event. The study will be restarted if the DSMB considers the serious adverse events to be unrelated to study drug.

The study will stop overall if any of the following occur:

1. The participant experiences a Serious Adverse Event (SAE) that, in the opinion of the investigator, is possibly, probably or definitely related to the study drug utilizing the National Cancer Institute's CTCAE system as a guide.

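### Section 4.4.1 replaces every withdrawn patient until 10 complete, whatever the reason, with no maximum and no link to MELD-Na phase; this cannot be carried out alongside the 8.5 stop for a related SAE and leaves the five-plus-five step undefined

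*Combined protocol and SAP*

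**What the plan says.** All references are to the combined protocol and SAP.

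- **Replacement (4.4.1).** After ten numbered withdrawal reasons the section says: "If subjects are withdrawn from the study, they will be replaced to ensure a total of 10 patients complete the study in its entirety". The reasons include item 3, "Subjects experience a serious adverse event felt to possibly be related to acamprosate administration as determined by PI and/or DSMB"; item 5, "Exhibition of unacceptable toxicity which would make it difficult or dangerous to comply with further protocol requirements"; item 7, "Death of the subject"; and item 10, a complication that the investigator attributes to the drug. The sentence that follows keeps withdrawn patients' data up to withdrawal in the analysis.
- **Sample size.** Section 3.2 says "10 individuals" and the Study Summary gives the same number. Neither says whether these are enrolled, dosed or completing. Section 7.1 reports no power analysis.
- **Phases.** Section 1.1 plans "an initial pilot study in five patients with a Model for End Stage Liver Disease Sodium (MELD-Na) score less than 20 will be conducted", then five patients at MELD-Na 20 or more if no safety concern is found. Section 3.1 says "initial MELD-Na score must be less than 20 for the five individuals enrolling in the first phase of the pilot safety assessment"; sections 3 and 4.1 say the same.
- **Stopping (8.5).** Any SAE puts the study on hold, with restart if the DSMB finds it unrelated. A separate list opens with "The study will stop overall if any of the following occur". Its first item is an SAE that the investigator considers at least possibly related; its second is two or more patients with attributable grade 3 or higher events.
- **Analysis set (7.3).** Everyone who took at least one dose.

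**The concern.** Replacement is normally meant for patients who leave without answering the study's question. Here the question is safety and tolerability, and a patient withdrawn for death, toxicity or a related event has answered it. A rule that replaces such patients, without limit, exposes another person to the drug because an earlier one was harmed.

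The rule also meets two other parts of the protocol that were not written with it in mind. One is the set of study-level stops in 8.5. The other is the two-phase design, in which the move to sicker patients, and later to a placebo-controlled study, depends on a first phase of five. If staff cannot tell whether a withdrawal leads to a stop or to a replacement, or which phase the replacement joins, the safety step can be run in more than one way.

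**Working it through.** **1. The plan's own figure.** 5 + 5 = 10, which matches 3.2 and the Study Summary. It is a count of patients with no power calculation behind it, so nothing statistical depends on having 10 completers.

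**2. Section 4.4.1 against 8.5, by type of event.**

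| Event | 4.4.1 | 8.5, study level | Compatible? |
|---|---|---|---|
| SAE the investigator judges at least possibly related (item 3; also a related death, or an item 10 event that prolongs hospitalization) | withdraw and replace | study stops (overall item 1) | No |
| Death or other SAE the DSMB finds unrelated | replace, if withdrawn | hold, then restart | Yes, after restart |
| Attributable grade 3 or higher event, not an SAE, one patient | replace, if withdrawn | individual stop only | Yes |
| The same in two or more patients | replace | study stops (overall item 2) | No, from the second patient |
| Lesser toxicity, non-compliance, lost to follow-up | replace | no rule | Yes |

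Section 8.5 also names the related SAE in its list of individual stops (item 2), in the same terms as overall item 1. If the study always stops for that event, the individual rule adds nothing. Part of the inconsistency therefore lies within 8.5.

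How often this could matter depends on q, the chance that one patient has a related SAE. The documents do not give q. With independent patients, the chance of at least one is 1 − (1 − q)^n:

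| Assumed q | n = 5 | n = 10 |
|---|---|---|
| 1% | 5% | 10% |
| 5% | 23% | 40% |
| 10% | 41% | 65% |
| 20% | 67% | 89% |

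**3. Section 4.4.1 against the phases.** Suppose one of the first five is withdrawn. If the replacement has MELD-Na below 20, six have enrolled in a phase described as five enrolling. If the replacement has MELD-Na 20 or more, four complete the first phase. No text chooses between these.

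**4. Number dosed.** Let w be the assumed chance that a dosed patient is withdrawn. The documents give no value. Ignoring study-level stops, recruitment until 10 complete gives:

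- expected number dosed = 10/(1 − w);
- chance that exactly 10 are dosed = (1 − w)^10;
- chance that exactly five are dosed in a five-completer first phase = (1 − w)^5.

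| w | Expected dosed | Exactly 10 | Exactly 5 in first phase |
|---|---|---|---|
| 10% | 11.1 | 35% | 59% |
| 20% | 12.5 | 11% | 33% |
| 30% | 14.3 | 3% | 17% |
| 40% | 16.7 | 0.6% | 8% |

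**5. Effect on the observed withdrawal rate.** With K withdrawals before the tenth completer (negative binomial), the observed rate among all dosed is K/(K + 10). Its mean is 28.0% when w = 30% and 37.7% when w = 40%, a shortfall of 2.0 and 2.3 percentage points.

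**The case against.** The strongest reply is that replacing dropouts is a defensible choice in a small unpowered pilot that wants 10 patients with full exposure and follow-up, and that 8.5 already limits the harm. A stopped study recruits nobody, any SAE brings a hold, and the DSMB can stop the study at any time. This stands in part: uncapped replacement can happen only inside those limits. It does not supply a maximum or a rule by phase, and it leaves the reader to infer that 8.5 overrides 4.4.1.

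Three stronger readings are tempting, and the documents do not support them.

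- *That 4.4.1 contradicts the stated sample size.* The number in 3.2 and the summary is undefined, and 4.4.1 can be read as making it a completer target. The clearer misfit is with the first phase, which is described as five enrolling.
- *That replacing any patient who dies or has toxicity breaches 8.5.* As the first table shows, an unrelated death leads to a hold and possible restart, and a single attributable grade 3 or higher event short of an SAE does not stop the study.
- *That replacement materially flatters tolerability.* Three toxicity withdrawals in 10 would become 3/13, or 23% instead of 30%, if three replacements all completed. That path also needs events below the 8.5 thresholds. Averaged over all paths the shortfall is about 2 points. Replacements can have events of their own, the analysis is descriptive, and 4.4.1 and 7.3 keep every dosed patient's data.

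**Conclusion.** The point holds, as a matter of conflicting and incomplete instructions and avoidable exposure, and not as a material bias. Three things are established from the text alone. Section 4.4.1 and overall item 1 of 8.5 cannot both be carried out for an SAE judged at least possibly related, and 8.5 is itself unclear about that event. Replacement does not fit a first phase of five enrolling. No maximum number dosed is stated.

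The size is an illustration. It rests on assumed withdrawal rates of 10 to 40%, the same for each patient and independent, with no study-level stop; on that basis 11.1 to 16.7 patients would be dosed on average for 10 completers. The judgement that replacing safety withdrawals brings little gain rests on the primary objective being safety and tolerability, and on those patients staying in the analysis. It should be settled before enrolment, because the step to MELD-Na 20 or more depends on it.

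**What to change.** In 4.4.1:

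- limit replacement to patients who were never dosed, or who were withdrawn for reasons unrelated to an adverse event;
- state that patients withdrawn for safety reasons count as evaluable for the primary endpoint and are not replaced. Say how a patient withdrawn for non-compliance under 5.5 is classed when side effects were the cause;
- replace only within the same MELD-Na phase.

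In 3.2 and the Study Summary, say whether 10 and five mean dosed or completing, whether completing means the end of treatment or the week 24 call, and give a maximum number dosed. Carry the same terms into 1.1, 3, 3.1 and 4.1.

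Reconcile 4.4.1 with the hold and stop provisions of 8.5, and the individual with the overall list inside 8.5, so that one event leads to one stated course. Which stopping rule should apply is for the sponsor and the DSMB to decide.

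The cost is protocol wording. The downside is fewer than 10 completers if safety withdrawals occur. That would itself be a safety result, and no power calculation depends on 10.
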